#### **6.2. Preparation/Handling/Storage/Accountability**

[figure not shown]
The investigator or an approved representative, eg, pharmacist, will ensure that all study interventions are stored in a secured area with controlled access under required storage conditions and in accordance with applicable regulatory requirements.

Study interventions should be stored in their original containers and in accordance with the labels.

CCI

CCI

Upon identification of a product complaint, notify the sponsor within 1 business day of discovery as described in the IP manual.

#### **6.2.1. Preparation and Dispensing**

See the IP manual or applicable SRSD for instructions on how to prepare the study intervention for administration. Study intervention should be prepared and dispensed by an appropriately qualified and experienced member of the study staff (eg, physician, nurse, physician's assistant, nurse practitioner, pharmacy assistant/technician, or pharmacist) as allowed by local, state, and institutional guidance. A second staff member will verify the dispensing.

Study intervention will be prepared by qualified site personnel according to the IP manual. The study intervention will be administered to blinded participants.

### **6.3. Measures to Minimize Bias: Randomization and Blinding**

#### **6.3.1. Allocation to Study Intervention**

Allocation of participants to vaccine groups will proceed through the use of an IRT system (IWR). The site personnel (study coordinator or specified designee) will be required to enter or select information including but not limited to the user's ID and password, the protocol number, and the participant number. The site personnel will then be provided with a vaccine assignment, randomization number, and DU or container number when study intervention is being supplied via the IRT system. The IRT system will provide a confirmation report containing the participant number, randomization number, and DU or container number assigned. The confirmation report must be stored in the site's files.

Study intervention will be dispensed at the study visits summarized in the SoA.

Returned study intervention must not be redispensed to the participants.

An otherwise uninvolved third party (unblinded site staff) will be responsible for the second administration of the study intervention (saline or PPSV23) at Vaccination 2 (Visit 2). This includes ensuring that there are no differences in time or effort taken to administer the study intervention and no blinded site staff or participants are able to view the administration (refer to the SRM for details).

The study-specific IRT reference manual and IP manual will provide the contact information and further details on the use of the IRT system.

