## 4. STUDY DESIGN

### 4.1. Overall Design

This will be a Phase 3, multicenter, randomized, double-blind third-party–unblinded study that will be conducted at investigator sites in Japan, Korea, and Taiwan.

Approximately 1400 participants 60 years of age and older who are pneumococcal vaccine naïve will be randomized into 2 vaccine groups in a 1:1 ratio. Each participant will receive either 20vPnC or 13vPnC (control vaccine) at Vaccination 1. Participants who received 20vPnC at Vaccination 1 will receive saline at Vaccination 2. Participants who received 13vPnC at Vaccination 1 will receive PPSV23 at Vaccination 2.

On Day 1 (Visit 1), participants will be assessed for eligibility, have blood drawn for immunogenicity assessments, and receive 20vPnC or 13vPnC administered by blinded site staff. Participants will be observed for at least 30 minutes after vaccination by blinded site staff, who will record AEs occurring during that time. Participants will also receive safety follow-up and e-diary instructions at the visit. Prompted systemic events (fever, headache, fatigue, muscle pain, and joint pain) occurring within 7 days after vaccination (where Day 1 is the day of vaccination) and prompted local reactions (redness, swelling, and pain at the injection site) occurring at the 20vPnC or 13vPnC injection site within 10 days after vaccination (where Day 1 is the day of vaccination) will be collected daily in the e-diary. Use of antipyretic/pain medications will be collected daily in an e-diary for 7 days after vaccination (where Day 1 is the day of vaccination). Participants will be instructed to contact the study staff if the participant experiences redness or swelling at the 20vPnC/saline injection site measuring >20 measuring device units (>10 cm) or severe injection site pain (prevents daily activity) in the 10 days after vaccination or has an emergency room visit or hospitalization.

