#### **6.3.2. Blinding of Site Personnel**

Site personnel taking part in any participant randomization, assessments, interviews, data collection, or CRF data entry, including the PI, will be blinded to study intervention assignments during the study.

At Vaccination 1, 20vPnC or 13vPnC will be administered in a double-blind fashion, as the appearance and PFSs of 20vPnC and 13vPnC are identical (PFSs packaged in blinded cartons).

At Vaccination 2, saline and PPSV23 will be prepared and administered by a third-party unblinded site staff member. All other study personnel, including the PI, and the participant, will be blinded. The unblinded site staff member(s) will not participate in participant assessments.

The PI will assign the responsibility of administering saline and PPSV23 to third-party unblinded site staff who will not participate in the evaluation of any study participant. More than 1 unblinded site staff member will be assigned. A member of the study site staff or

clinic pharmacy should fulfill this role. Contact between the unblinded staff member who will administer saline and PPSV23 and study participants should be kept to a minimum.

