**8.11.1. Visit 1 (Vaccination 1 – Day 1)**

Prior to vaccination:

- Obtain a personally signed and dated ICD indicating that the participant has been informed of all pertinent aspects of the study before performing any study-specific procedures.
- Assign a participant number via the IRT.
- Obtain and record the participant demography (sex, date of birth, ethnicity, and race). The complete date of birth (ie, DD-MMM-YYYY) will be collected to critically evaluate the immune response and safety profile by age.

- Obtain and record significant medical history including the presence of chronic conditions (eg, diabetes, asthma, cardiac disease, COPD, renal disorders) and/or medical history of significance such as relevant surgical procedures.
- Conduct a clinical assessment. If the clinical assessment indicates that a physical examination is necessary to comprehensively evaluate the participant, perform a physical examination and record any findings in the source documents and, if significant, record on the medical history CRF.
- Assess and record smoking history.
- Record details of any medications currently being taken for any medical conditions.
- Record nonstudy vaccinations and medications as described in [Section 6.5.3](#).
- Measure and record the participant's height, weight, and oral temperature (°C).
- Instruct the participant to use appropriate contraceptives until 28 days after Vaccination 2, if applicable, and document the conversation and the participant's affirmation in the participant's chart.
- Ensure and document that all of the inclusion criteria and none of the exclusion criteria are met and that none of the temporary delay criteria are met.
- Assign a randomization number and a study intervention container number via the IRT. This must be the last step before proceeding. A site staff member will prepare the study intervention according to the IP manual.

After randomization:

- Collect a blood sample of approximately 30 mL for immunogenicity assessments prior to vaccination.
- Administer a single 0.5-mL injection of study intervention (20vPnC or 13vPnC) into the deltoid muscle of the nondominant arm.

After vaccination:

- Blinded site staff will observe the participant for 30 minutes after study intervention administration for any reactions. Record any AEs on the CRF and on the Vaccine SAE Reporting Form as applicable. Record concomitant medications used to treat SAEs.

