2.2. Study Design

This Phase 3, multicenter, randomized, double-blind study will be conducted at investigator sites in Japan, Korea, and Taiwan.

Approximately 1400 participants 60 years of age and older at enrollment will be randomized into 2 groups in a 1:1 ratio by center-based randomization, stratified by age (60 through 64 years of age and ≥ 65 years of age), and assigned to either the 20vPnC/saline group or the 13vPnC/PPSV23 group. Each participant will be randomized to receive either 20vPnC or 13vPnC (control vaccine) at Vaccination 1. Participants who receive 20vPnC at Vaccination 1 in the 20vPnC/saline group will receive saline at Vaccination 2. Participants who received 13vPnC at Vaccination 1 in the 13vPnC/PPSV23 group will receive PPSV23 at Vaccination 2.

On Day 1 (Visit 1), participants will be assessed for eligibility, have blood drawn for immunogenicity assessments, and receive 20vPnC or 13vPnC administered by blinded or unblinded site staff. Participants will be observed for at least 30 minutes after vaccination by blinded site staff, who will record AEs occurring during that time. Participants will also receive safety follow-up and e-diary instructions at the visit. Prompted systemic events (fever, headache, fatigue, muscle pain, and joint pain) occurring within 7 days after vaccination and prompted local reactions (redness, swelling, and pain at the injection site) occurring at the 20vPnC or 13vPnC injection site within 10 days after vaccination will be collected daily in the e-diary. Use of antipyretic/pain medications will be collected daily in an e-diary for 7 days after vaccination.

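### Does the IRT text in Protocol 6.3.1 unblind the site staff who randomise participants and record adverse events?

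*Protocol*

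**What the plan says.** **IRT allocation (Protocol 6.3.1).** The user is the coordinator or a designee: "The site personnel (study coordinator or specified designee) will be required to enter or select information". The section then states: "The site personnel will then be provided with a vaccine assignment, randomization number, and DU or container number". On the record kept at the site it says: "The IRT system will provide a confirmation report containing the participant number, randomization number, and DU or container number assigned".

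**Blinding rule (Protocol 6.3.2).** "Site personnel taking part in any participant randomization, assessments, interviews, data collection, or CRF data entry, including the PI, will be blinded". For Vaccination 1 the same section explains that "the appearance and PFSs of 20vPnC and 13vPnC are identical (PFSs packaged in blinded cartons". For Vaccination 2, saline and PPSV23 are prepared and given by third-party unblinded staff who take no part in assessments. Everyone else at the site, the principal investigator included, stays blinded.

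**Visit 1 procedure (Protocol 8.11.1).** "Assign a randomization number and a study intervention container number via the IRT".

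**Who gives Vaccination 1.** Protocol 4.1 has participants "receive 20vPnC or 13vPnC administered by blinded site staff", and the synopsis and 6.1.1 agree. SAP 2.2 has them "receive 20vPnC or 13vPnC administered by blinded or unblinded site staff".

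**The concern.** Section 6.3.1 lists a vaccine assignment as an item separate from the randomisation and container numbers. It names as recipient a coordinator who may also interview participants and complete the CRF. If the IRT screen showed which vaccine had been allocated, that person could not be blinded as 6.3.2 requires. Because the sequences are fixed (20vPnC then saline, 13vPnC then PPSV23), knowing the first product reveals the second.

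The stake would be the part of primary safety that relies on site judgement: adverse events within 1 month of 20vPnC or 13vPnC, whose intensity and causality the investigator assesses (Protocol 10.3.3). A second route would be the eligibility check before Vaccination 2 (Protocol 7.1). Receipt of the second injection is required for the evaluable 7-additional population only in the 13vPnC/PPSV23 group (Protocol 9.3, SAP 4), so informed decisions at Visit 2 could alter that population differently by arm. The SAP sentence on who injects at Visit 1 appears to loosen the blind further.

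**Working it through.** No arithmetic applies: the point depends on no error rate, margin, variance or sample size. The check is to set the relevant places side by side and ask whether a site following all of them would learn the vaccine's identity.

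**A. What the IRT returns at Visit 1**

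| Place | What it implies for the randomising user |
|---|---|
| Protocol 6.3.1, allocation sentence | An assignment plus two numbers; does not say whether the assignment is masked |
| Protocol 6.3.1, confirmation report | Participant, randomisation and DU/container numbers; no vaccine named |
| Protocol 8.11.1 | Randomisation number and container number; no vaccine named |
| Protocol 6.3.2 | The person randomising is blinded; syringes identical, cartons blinded |
| Protocol 6.4 | The check at dosing treats the product as blinded |
| Protocol 6.3.4 | Assignment is revealed by an emergency procedure, with sponsor notification within 24 hours and an entry in source documents and CRF |

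One sentence is open to an unblinding reading, and the other five entries describe or presuppose a masked process. The emergency procedure would have no purpose if coordinators routinely saw the vaccine's name. The allocation sentence is compatible with the rest if the assignment is expressed to the blinded user through the container number, which is all that is needed to pick the right carton. So the conflict is one of wording, and unblinding follows only under the added premise that the IRT displays vaccine identity to blinded users. No place in either document says that it does. Section 6.3.1 leaves the details of IRT use to the IRT reference manual and the IP manual.

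**B. Who gives Vaccination 1**

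1. Protocol synopsis, 4.1 and 6.1.1: blinded staff.
2. SAP 2.2: blinded or unblinded staff.
3. SAP 2.2, next sentence: observation after vaccination and recording of adverse events are done by blinded staff.
4. Protocol 6.1.1 and 6.3.2: unblinded staff take no part in assessments.

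Item 2 differs from item 1, but items 3 and 4 separate the person who injects from the person who records. An unblinded colleague giving an identical-looking syringe does not tell the recorder what it contains. The SAP sentence is a summary of study design with no analysis attached, and the protocol governs who vaccinates.

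**C. What would be exposed even under the unproven premise**

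- Two of the four primary safety components, prompted local reactions and prompted systemic events, are recorded by blinded participants in the e-diary (Protocol 8.2.1). The exception is Grade 4 events, which the investigator classifies.
- Primary safety is described without a hypothesis test (Protocol 1.1 and 9.4.2).
- OPA titres come from laboratory personnel who remain blinded throughout (Protocol 6.3.3).
- That leaves investigator-assessed adverse events and serious adverse events, and the indirect route through eligibility at Visit 2.

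**The case for a change.** The strongest reply is that the protocol's own vocabulary favours the literal reading. Section 6.3.4 uses the same term, vaccine assignment, for exactly what blind-breaking discloses, and 6.3.1 lists it apart from the two numbers. Visit 2 is also less well covered. The identical syringes and blinded cartons protect Vaccination 1 only, 6.3.1 names a single type of IRT user, the Visit 2 procedure (8.11.2) has no IRT step, and nothing states that output identifying saline or PPSV23 goes only to unblinded staff. The remedy would be a few words.

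Part of this stands. The phrase in 6.3.1 is loose and unnecessary, and the documents do not settle what each IRT role sees. But 6.3.4 cuts both ways: it uses the term for identity and in the same breath treats identity as concealed by default. At Visit 2, 6.1.1 and 6.3.2 already confine preparation and administration to third-party unblinded staff and blind everyone else. Output that names the product therefore has only one place it can properly go. What remains is a query about system permissions, answered by the IRT set-up and manuals. The arguments about biased adverse event reporting and altered evaluable populations all depend on the identity display that has not been shown.

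**Conclusion.** The concern does not call for a change to the plan. There are two wording mismatches: the assignment phrase in Protocol 6.3.1 against the blinding rule in 6.3.2, and SAP 2.2 against the protocol on who gives Vaccination 1. Each is resolved by the more specific text around it. The plan states a masked design for all site personnel except the third-party staff at Vaccination 2, and rewording would only bring two sentences into line with that design. No endpoint, population, model or decision rule would differ.

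No numerical size can be given. The phrase touches all of the approximately 1400 randomisations, but its effect on the blind is nil if the IRT follows 6.3.2 and 8.11.1. The conclusion assumes that set-up, and that PPSV23/saline allocation reaches only the unblinded staff. Neither can be confirmed without the IRT and IP manuals. If the IRT did show vaccine identity to blinded users, that would be a failure to follow 6.3.2, not a consequence of the stated design.

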#### **6.3.2. Blinding of Site Personnel**

Site personnel taking part in any participant randomization, assessments, interviews, data collection, or CRF data entry, including the PI, will be blinded to study intervention assignments during the study.

At Vaccination 1, 20vPnC or 13vPnC will be administered in a double-blind fashion, as the appearance and PFSs of 20vPnC and 13vPnC are identical (PFSs packaged in blinded cartons).

At Vaccination 2, saline and PPSV23 will be prepared and administered by a third-party unblinded site staff member. All other study personnel, including the PI, and the participant, will be blinded. The unblinded site staff member(s) will not participate in participant assessments.

The PI will assign the responsibility of administering saline and PPSV23 to third-party unblinded site staff who will not participate in the evaluation of any study participant. More than 1 unblinded site staff member will be assigned. A member of the study site staff or

clinic pharmacy should fulfill this role. Contact between the unblinded staff member who will administer saline and PPSV23 and study participants should be kept to a minimum.

### **6.3.3. Blinding of the Sponsor**

Those study team members who are involved in ensuring that protocol requirements for study intervention handling, allocation, and administration are fulfilled at the site (eg, study manager, CRAs, and unblinded medical monitor) will be unblinded for the duration of the study. All other study team members and all laboratory personnel performing the serology assays will remain blinded to vaccine assigned/received throughout the study.

### **6.3.4. Breaking the Blind**

The study will be participant- and investigator-blinded through the duration of the study.

The IRT will be programmed with blind-breaking instructions. In case of an emergency, the investigator has the sole responsibility for determining if unblinding of a participant's vaccine assignment is warranted. Participant safety must always be the first consideration in making such a determination. If the investigator decides that unblinding is warranted, the investigator should make every effort to contact the sponsor prior to unblinding a participant's vaccine assignment unless this could delay further management of the participant. If a participant's vaccine assignment is unblinded, the sponsor must be notified within 24 hours after breaking the blind. The date and reason that the blind was broken must be recorded in the source documentation and CRF.

The study-specific IRT reference manual and IP manual will provide the contact information and further details on the use of the IRT system.

## **6.4. Study Intervention Compliance**

All doses of study intervention will be administered by the appropriately designated study staff at the investigator site. The date and time of each dose administered will be recorded in the source documents and recorded in the CRF. The blinded study intervention and study participant ID will be confirmed at the time of dosing by a member of the study site staff other than the person administering the study intervention.

## **6.5. Concomitant Therapy**

### **6.5.1. Prohibited Concomitant Vaccines and Treatments**

- Receipt of any investigational vaccines, drugs, or medical devices is prohibited during a participant's participation in the study.
- Receipt of nonstudy pneumococcal vaccine is prohibited during participant participation in the study.
- Receipt of blood/plasma products, immunoglobulins, and/or immunosuppressive therapy (including a  $\geq 14$ -day course of systemic corticosteroids) is prohibited during study participation.

### **6.5.2. Permitted Concomitant Vaccines and Treatments**

- Prescription and nonprescription medications, vitamins, minerals, and herbal remedies are permitted during a participant's participation in the study.
- Licensed inactivated influenza vaccine may be given >14 days prior to or >14 days after study intervention administration.
- If medically necessary (eg, pandemic or outbreak with pandemic potential), licensed influenza or other pandemic vaccines may be given at any time (however, an interval of >14 days prior to or >14 days after study intervention administration is preferred).
- Receipt of other licensed nonstudy vaccine (except pneumococcal [prohibited] or influenza or pandemic vaccine [permitted] as described above) is permitted after Visit 3.
- The use of prophylactic antipyretic medication, while permitted, is not recommended on the day prior to vaccination or the day of study intervention administration.
- Inhaled/nebulized, topical (skin, eyes, or ears), or localized injections of corticosteroids (eg, intra-articular or intrabursal administration) are permitted during a participant's participation in the study.

### **6.5.3. Recording Concomitant Vaccines and Treatments**

The name and date of administration for any nonstudy vaccinations received from the time of signing of the ICD to the final visit will be collected and recorded in the CRF.

Details of any medications that the participant is currently taking for medical conditions at enrollment will be recorded in the CRF.

Medications taken to treat SAEs from the time of signing of the ICD to the final visit will be recorded in the CRF.

### **6.6. Dose Modification**

Not applicable.

### **6.7. Intervention After the End of the Study**

No intervention will be provided to study participants at the end of the study.

## **7. DISCONTINUATION OF STUDY INTERVENTION AND PARTICIPANT DISCONTINUATION/WITHDRAWAL**

### **7.1. Discontinuation of Study Intervention**

Participant eligibility must be confirmed prior to each vaccination in order to continue in the study.

If a participant no longer meets the eligibility criteria during the vaccination period of the study, further vaccinations should be discontinued, but the participant may remain in the study. If a participant is discontinued from vaccination and the participant consents, safety follow-up will be conducted as per [Section 8.3](#) (AEs and SAEs will be collected for 1 month after the last study vaccination).

In rare instances, it may be necessary for a participant to permanently discontinue study intervention (definitive discontinuation). Reasons for definitive discontinuation of study intervention include the following: the participant no longer meets eligibility criteria, specific protocol deviations, withdrawals by the participant, and certain AEs or SAEs.

Note that discontinuation of study intervention does not represent withdrawal from the study. If study intervention is definitively discontinued, the participant will remain in the study to be evaluated for safety. See the SoA for data to be collected at the time of discontinuation of study intervention and follow-up for any further evaluations that need to be completed.

In the event of discontinuation of study intervention, it must be documented on the appropriate CRF/in the medical records whether the participant is discontinuing further receipt of study intervention or also from study procedures, postvaccination study follow-up, and/or future collection of additional information.

